**Study of Humidified Air to Improve Mucociliary Clearance (MCC) in COPD:**

**NCT03935932**

[name]., [name].  
Pulmonary, Allergy and Critical Care Medicine  
University of Pittsburgh

**Hypothesis:** The delivery of humidified air by nasal cannula will result in real-time improvement in mucociliary clearance.

**Intervention:** Delivery of humidified air using Fisher and Paykel myAirvo 2 and Optiflow nasal cannula for 4 hours at 30 L/min, reduced to 25 L/min if required for tolerance and 37 degrees C.

**Population:** n=12, female or male subjects 40 – 85 years of age with chronic bronchitis

**Inclusion criteria:**

- (1) Male or Females 40 to 85 years old
- (2) Diagnosis of chronic bronchitis
- (3) Able to regularly produce sputum
- (4) Clinically stable
- (5) Current smoker or ex-smoker with a tobacco history of  $\geq 10$  pack-years (1 pack year = 20 cigarettes smoked per day for 1 year)
- (6) History of moderate to very severe COPD with a post-bronchodilator FEV1/FVC $<0.70$  and a post-bronchodilator FEV1 $>20\%$  and  $\leq 70\%$  of predicted normal value at enrollment. (5) CAT score  $\geq 10$ , with questions 1 and 2 responses  $\geq 5$

**Exclusion criteria:**

- (1) Pregnant or nursing or unwilling to perform pregnancy testing
- (2) Unwilling or unable to refrain for SABA/LABA use ahead of the study
- (3) Unable to lie recumbent for 90 min
- (4) Clinically important pulmonary disease other than COPD (e.g. active lung infection, clinically significant bronchiectasis, pulmonary fibrosis, cystic fibrosis, hypoventilation syndrome associated with obesity, lung cancer, alpha 1 anti-trypsin deficiency and primary ciliary dyskinesia) or another diagnosed pulmonary or systemic disease that is associated with elevated peripheral eosinophil counts (e.g. allergic bronchopulmonary aspergillosis/mycosis, Churg-Strauss syndrome, hyper-eosinophilic syndrome) and/or radiological findings suggestive of a respiratory disease other than COPD that is contributing to the subject's respiratory symptoms.
- (5) Any disorder, including, but not limited to, cardiovascular, gastrointestinal, hepatic, renal, neurological, musculoskeletal, infectious, endocrine, metabolic, hematological, psychiatric, or major physical impairment that is not stable in the opinion of the Investigator and/or could:
  - Affect the safety of the subject throughout the study
  - Influence the findings of the study or their interpretation
  - Impede the subject's ability to complete the entire duration of study
- (6) Treatment with systemic corticosteroids and/or antibiotics, and/or hospitalization for a COPD exacerbation within 2 weeks prior to enrollment, based on last dose of steroids or last date of hospitalization whatever occurred later
- (7) Acute upper or lower respiratory infection within 2 weeks prior to enrollment

(8) Supplemental oxygen use at greater than 3L/min

**Study procedures:**

**MCC assessment**

- 1) Subjects will perform 2 MCC assessment study days. One to measure baseline MCC and the other to measure MCC during treatment with the cannula. Study days will be separated by 4-7 days. The order of the days will be randomized. Subjects will refrain from SABA use for 6 hours and LABA/LAMA use for 24 hours prior to Visits 2 and 3.
- 2) Subjects will arrive in nuclear medicine. They will lie recumbent in the nuclear medicine camera while background images are collected. They will then perform a Cobalt-57 transmission scan which allows for visualization of the lung outlines. Both scans are utilized during image analysis.
- 3) Subjects will be seated for the inhalation of the radiolabeled particles. 4 mCi of Technetium 99m sulfur colloid (Tc-SC) in 2ml of saline will be added to a DeVilbiss 646 Nebulizer driven by a DeVilbiss 8650D compressor and attached to a Spira Dosimeter. Using standardized procedures developed the Cystic Fibrosis Foundation (1), we will deliver the aerosol for 5 approximately minutes using a specified breathing pattern (30 breaths/minute) using inhalation flowrates of ~0.5 L/s.
- 4) Subjects will then return to the camera and lie recumbent while serial two-minute gamma camera images are collected for 90 minutes. On the intervention day, the nasal cannula will be applied after 5 images are collected. On the baseline day there will be no intervention. Coughs will be manually logged by study personnel.
- 5) After 90 minutes the subjects will exit the camera and remain in the waiting areas around radiology. They will continue inhaling from the cannula on the intervention day. Subjects will perform a 10 minute follow up image at t=4 hours and 10 minutes after the start of the imaging sequence. The 10 minute image may be delayed for several minutes if the gamma camera is in use at the specified time Subjects would resume their normal medications.
- 6) We will plot normalized retention vs. time and compare the percentage of deposited material cleared at t=90 min and up to 6 hours on the intervention days. Areas above the curve 90 min clearance curve will also be compared. We will calculate the central deposition percentage of the Tc-SC aerosol to ensure that Tc-SC aerosol delivery was similar on both testing days.
- 7) Previous measurements from our group demonstrated a standard deviation of the intrasubject differences in MCC measurements ( $\sigma$ ) = 7.7% (2). Assuming  $\alpha=0.05$ ,  $\beta=0.2$ , and  $n=12$  matched pairs, we could detect a 6.8% (absolute) change in MCC rates via paired t-test. Average MCC rates in control subjects over 90 minutes have been reported to be 28.2% (1). MCC rate differences reported by Hasani et al were approximately 8% after 7 days of daily therapy (3).
- 8) We will replace subjects who do not complete both testing days until we have a total of 12 subjects with completed studies.

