### **Schedule of Assessments**

#### **Visit schedule**

	Visit 1	Visit 2	Visit 3
Baseline MCC*		X	
Treatment MCC*			X
Questionnaires	X		
Pre and Post Bronchodilator Spirometry	X		

\* Baseline and Treatment MCC are randomized.

The Fisher and Paykel myAirvo2 heater/humidifier and Optiflow nasal cannula are commercially available devices that are used together to deliver heated humidified air or oxygen for breathing. The purpose of this study is to determine whether 4 hours of use of this device will improve mucus clearance in patients with chronic bronchitis. This may occur through hydration of airway secretions and possibly through splinting of the airways. Twelve subjects will be enrolled and perform two imaging days and a possible screening day. The primary outcome measure is mucociliary clearance as measured using a nuclear medicine imaging technique.

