Study of Humidified Air to Improve Mucociliary Clearance (MCC) in COPD:

NCT03935932

[name]., [name].
Pulmonary, Allergy and Critical Care Medicine
University of Pittsburgh

June 5, 2023

Statistical Analysis Plan:

We will plot normalized retention vs. time and compare the percentage of deposited material cleared at $t=90$ min and up to 6 hours on the intervention days. Areas above the curve 90 min clearance curve will also be compared. We will calculate the central deposition percentage of the Tc-SC aerosol to ensure that Tc-SC aerosol delivery was similar on both testing days.

Statistical comparisons will be made using paired non-parametric statistics to compare the baseline clearance day to the Airvo clearance day (Wilcoxon Signed Rank).

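### Optional improvement: day order is randomised but neither balanced nor used in the analysis; a 6:6 allocation with an exact test by order would protect power against a visit-to-visit shift

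*Protocol*

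**What the plan says.** Protocol, Study procedures, MCC assessment, item 1 gives each subject two imaging days, one without and one with the cannula, and states "The order of the days will be randomized". The Schedule of Assessments table prints baseline under Visit 2 and treatment under Visit 3, but its footnote confirms "Baseline and Treatment MCC are randomized". No allocation ratio, blocking or method is given.

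Item 7 sizes the trial on the "standard deviation of the intrasubject differences in MCC measurements", put at 7.7%. With 12 pairs, alpha 0.05 and 80% power it concludes "we could detect a 6.8% (absolute) change in MCC rates via paired t-test". Item 8 adds "We will replace subjects who do not complete both testing days until we have a total of 12 subjects with completed studies". It does not say which order a replacement receives.

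The SAP names one test: "Statistical comparisons will be made using paired non-parametric statistics to compare the baseline clearance day to the Airvo clearance day (Wilcoxon Signed Rank". No order, visit or period term appears in either document.

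**The concern.** Randomising order stops a shift in MCC between the two visits from biasing the comparison on average. It does not remove the spread that the shift creates. If MCC moves by P points from Visit 2 to Visit 3, subjects treated second show the effect plus P and subjects treated first show the effect minus P. A pooled test counts that spread as noise, although the order of every subject is known.

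With 12 completers and power set at 80% there is little room for avoidable variance. Removing it needs no extra subject, scan or visit, but it works well only if the orders are balanced, and nothing in the plan secures that.

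**Working it through.** 1. **The plan's own figure.** Inputs from item 7: SD 7.7, n = 12, alpha 0.05, power 0.80. A two-sided paired t-test (noncentral t, 11 df) gives a detectable change of 6.84 points, and power of 79.5% at 6.8. The stated 6.8% is reproduced. Sidedness is not stated, but a one-sided test would give 5.90, so two-sided is used throughout.

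2. **Model.** Let s = +1 if treatment is second and −1 if first. Visit 3 minus Visit 2 is P + s·Δ + error, so treatment minus baseline is D = Δ + s·P + error, with error SD 7.7. At 6:6 the P terms cancel in the mean of D, but the pooled SD becomes √(7.7² + P²): √63.29 = 7.96 at P = 2, √68.29 = 8.26 at P = 3, √75.29 = 8.68 at P = 4. Comparing the visit differences between orders gives 2Δ, and P drops out.

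3. **Power at 6:6, with P added to the SD of 7.7.** Simulation with Δ = 6.8, normal errors, two-sided 0.05, an exact signed-rank test, a permutation test over all 924 arrangements, and 100,000 trials per row. P is an assumption.

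| P | Signed-rank | Paired t | Linear model by order | Permutation by order |
|---|---|---|---|---|
| 0 | 75.2% | 79.5% | 78.6% | 78.3% |
| 1 | 74.9% | 79.1% | 78.8% | 78.5% |
| 1.5 | 73.9% | 78.2% | 78.6% | 78.3% |
| 2 | 72.9% | 77.6% | 78.9% | 78.6% |
| 3 | 69.8% | 74.7% | 78.8% | 78.5% |
| 4 | 65.1% | 70.6% | 78.6% | 78.3% |

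4. **Separating order from ranks.** The 3-point gap at P = 0 (78.3 − 75.2) is means against ranks. The like-for-like effect of order adjustment is linear model minus paired t: −0.9, −0.3, +0.4, +1.3, +4.1 and +8.0 points down the table. It breaks even between P = 1 and P = 1.5. A rank-sum test by order has about 73% power at every P, which is below signed-rank at P = 0 and level with it at P = 2.

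5. **If 7.7 already contains P.** The residual SD is √(7.7² − P²) = 7.44, 7.09 and 6.58 at P = 2, 3 and 4. Signed-rank power is then 75.8, 76.1 and 76.5%, so nothing is lost against its value at P = 0. The permutation test would reach 81.3, 84.5 and 89.3%.

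6. **Balance.** Under unrestricted 1:1 randomisation an exact 6:6 split has probability 924/4096 = 22.6%, and 8:4 or worse has 1 − (792 + 924 + 792)/4096 = 38.8%. Permutation power is 77.2% at 7:5, 73.2% at 8:4 and 66.3% at 9:3. Averaged over such randomisation it is about 74% at any P, against 75.4, 72.4, 69.1 and 64.5% for signed-rank at P = 0, 2, 3 and 4.

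7. **Size of the planned test.** With 1:1 order the signed-rank test rejects a true null 4.2 to 4.3% of the time for P from 0 to 4. If each completer had a 70% chance of being treated second, size would be 5.3, 6.6 and 8.2% at P = 2, 3 and 4. From 1:1 assignment that requires treatment-first subjects to complete at 0.3/0.7 = 43% of the other order's rate, so at least 57% of them would not complete. At 60% the ratio is 0.4/0.6 = 67%, so at least 33% would not complete, and size is 4.5 to 5.2%.

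8. **Heavy tails** (scaled to SD 7.7, 6:6). With t errors on 3 df, signed-rank against permutation is 88.3 against 86.0% at P = 0, and 86.1 against 85.9% at P = 2. On 5 df with no shift it is 80.3 against 80.7%.

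**The case against.** The strongest reply is that nothing is broken. A signed-rank test on paired differences is a valid and common analysis of a small crossover with randomised order. The benefit of adjusting for order rests on a shift that the documents neither state nor suggest. They point to a small one: stable subjects, days less than about a week apart, the same bronchodilator withholding before both visits, and a check that aerosol deposition was similar. At a small shift most of the gain comes from replacing a rank statistic with a mean, which gives up some robustness. Without a 6:6 rule, the test by order is about a point worse than signed-rank at P = 0 and about 1.5 points better at P = 2.

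All of this stands, and it keeps the point optional. What remains is that balance and analysis by order, taken together, are no worse than the SAP's test at any shift when differences are normal, and clearly better if the shift turns out to be 3 points or more.

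A reader might also infer that the pooled test inflates type I error. The documents do not support that. Under 1:1 order it holds its level, and the skew needed to break it would take order-related non-completion far beyond anything the plan suggests. It is not a reason for the change.

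**Conclusion.** This is a cheap improvement, not an error. At 6:6, with SD 7.7, a true change of 6.8 points, normal differences and a constant shift that adds to the SD, testing by order gains about 3 points of power at P = 0, 6 at P = 2, 9 at P = 3 and 13 at P = 4. The low-P figures deserve most weight.

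A reader might take the whole gap as the price of ignoring order, or conclude that the trial is underpowered for that reason. Neither follows. About 3 points are unrelated to order, P is unknown, and the protocol does not say whether its SD already includes visit-to-visit variation. If it does, the plan forgoes a gain and loses nothing. Neither test addresses carry-over or drop-out that depends on the outcome.

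**What to change.** If orders are not yet drawn:

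- Allocate order 6:6 from a concealed list.
- Keep the 12 completers balanced when subjects are replaced, for example by giving a replacement the order of the subject replaced.
- Make the primary test an exact permutation test of Visit 3 minus Visit 2 differences between the two orders (smallest two-sided p = 2/924 = 0.002). Estimate the effect as the average of the two order-specific mean treatment differences, with a linear model on 10 df for the interval.
- Keep the pooled signed-rank test as sensitivity analysis.

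If orders were already drawn without balance, keep the signed-rank test as primary, report the realised split, and add the order-adjusted estimate as sensitivity analysis. The documents do not say which case applies.

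The cost is an allocation list and an SAP edit made before the data are seen. One degree of freedom is spent: the 95% interval half-width goes from 4.89 to 4.95 points, and linear-model power is about 1 point below the paired t-test when there is no shift. About 2 points of power are lost to signed-rank under very heavy tails with no shift. Power falls if balance is not kept. Replacement orders become somewhat predictable in a study where the cannula is visible to everyone, which is why the list should be concealed.

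### Does the plan need to name the image that counts as 100% retention, and should that be the mean of the five pre-cannula images?

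*Protocol*

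**What the plan says.** The Protocol's study summary, under the visit schedule, states: "The primary outcome measure is mucociliary clearance as measured using a nuclear medicine imaging technique". MCC assessment, item 6, and the SAP describe the computation in the same words: "We will plot normalized retention vs. time and compare the percentage of deposited material cleared". They apply it at 90 minutes and at a later time, and add a comparison of areas above the 90-minute curve. Neither document gives a reference image, an averaging window or a starting point for the area.

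The timing is given. Item 4 says "serial two-minute gamma camera images are collected for 90 minutes", which is 45 images if they are contiguous, and "On the intervention day, the nasal cannula will be applied after 5 images are collected". The baseline day has no intervention. Item 5 sets the clock for the late image: "Subjects will perform a 10 minute follow up image at t=4 hours and 10 minutes after the start of the imaging sequence". The standardised procedure is cited only for aerosol delivery: "Using standardized procedures developed the Cystic Fibrosis Foundation (1), we will deliver the aerosol".

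Item 7 sizes the trial on an SD of 7.7 points for within-subject differences, 12 pairs and a detectable change of 6.8 points. It also cites an average 90-minute clearance of 28.2% in control subjects. The SAP uses the Wilcoxon signed-rank test.

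**The concern.** Every clearance endpoint is a ratio, and its denominator is unnamed. Because the cannula starts after image 5, there are at least three untreated candidates: image 1, the mean of images 1 to 5, and image 5. They give different clearance levels and may differ in precision.

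Two things could be at stake in a 12-pair trial. A single-image denominator might waste precision when signed-rank power for 6.8 points at SD 7.7 is only about 75% under normality. And if the reference were chosen after the results were seen, taking the smallest of three p-values would raise the false-positive rate. On that reasoning the SAP should fix the five-image mean in advance.

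**Working it through.** **The plan's own figure.** Two-sided paired t-test, α = 0.05, power 0.80, n = 12, SD 7.7 (item 7). Solve P(|T| > 2.201) = 0.80 for a noncentral t with 11 degrees of freedom and noncentrality Δ√12/7.7. This gives Δ = 6.84 (noncentrality 3.08), and power at 6.8 is 79.5%. The stated 6.8 stands and does not depend on the reference, provided the 7.7 applies to the one used.

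**Effect of the reference on level and contrast.** Assume single-exponential clearance with 28.2% gone at 90 minutes: k = −ln(0.718)/90 = 0.00368 per minute. The reference retention r is exp(−k) = 0.996 for image 1 (mid-point 1 min), (1 − exp(−10k))/(10k) = 0.982 for the five-image mean, and exp(−9k) = 0.967 for image 5 (mid-point 9 min). Baseline clearance is 1 − 0.718/r, and a 6.8-point effect becomes 6.8/r.

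| Reference | Baseline clearance | Effect |
|---|---|---|
| Image 1 | 27.9% | 6.83 |
| Mean of 1–5 | 26.9% | 6.93 |
| Image 5 | 25.8% | 7.03 |

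With an assumed 15% fast-clearing fraction (half-life 5 minutes) the levels are 26.7%, 22.2% and 18.3%, and the effects 6.95, 7.37 and 7.74. The level moves, but the same divisor applies on both days and the contrast changes little.

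**Validity.** Images 1 to 5 are untreated on both days, so treatment cannot affect any of these denominators. Simulated under no effect, with the exact signed-rank test (reject at W ≤ 13, size 4.25%), each single reference rejects in 4.0 to 4.5% of trials.

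**Precision.** Treat the 7.7 as the SD with an image-1 reference, and split the variance 7.7² = 59.29 into image noise A and day-to-day rate variation B.

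- *Image noise, per-image CV c.* Two days with a numerator and a denominator each give A = (2 × 71.8c)² = (143.6c)². Averaging five reference images multiplies A by (1 + 1/5)/2 = 0.6. Image 5 leaves it unchanged.
- *Rate variation.* The SD is proportional to the interval from the reference to the last image (mid-point 89 min): 88, 84 and 80 minutes. B is multiplied by (84/88)² = 0.911 for the mean and (80/88)² = 0.826 for image 5.
- The factor 1/r multiplies effect and SD alike and cancels. The gain over image 1 is √[59.29/(0.6A + 0.911B)] for the mean and √[59.29/(A + 0.826B)] for image 5.

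| Image CV (assumed) | A | B | Mean of 1–5 | Image 5 |
|---|---|---|---|---|
| 0 | 0 | 59.29 | 1.048 | 1.100 |
| 1% | 2.06 | 57.23 | 1.054 | 1.096 |
| 2% | 8.25 | 51.04 | 1.073 | 1.084 |
| 5.4% | 59.29 | 0 | 1.291 | 1.000 |

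Simulations of this split at CVs of 0 to 2% put the mean's gain at 4 to 7%. A gain of 1.05 moves signed-rank power from about 75% to 79%. The two references tie when 0.4A = 0.085B, at c of about 2.2%. Below that, image 5 does better than the mean.

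**Plausibility of the top row of gains.** All-image noise needs c = 7.7/143.6 = 5.4%. If that were pure counting error it would mean 1/0.0536² ≈ 350 counts per two-minute image, about 3 per second, from a subject who inhaled from a 4 mCi load (148 million decays per second). The documents give no count rate and motion can add noise, but nothing points to this extreme.

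**Choosing after the fact.** Taking the smallest p of three references gives about 5% false positives at an image CV of 0.5%, 5.5% at 1% and 7% at 2%, against 4.25% for one reference. The 9.5% maximum again needs all of the SD to be image noise.

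**The case for a change.** The best case for acting is that the omission is real, concerns the primary outcome, and costs a sentence to repair. Across eight assumed noise models the five-image mean never fell below image 1 at 90 minutes. Its worst shortfall against the best reference was 1.047/1.100 = 0.95, against 1/1.297 = 0.77 for either single image. If the reference differed between days, a true 6.8-point effect could read anywhere from 2.9 to 11.4 in the curves tried.

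The omission stands. The rest weighs less.

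- A different denominator on each day would be a plain analysis error. A paired comparison of normalised curves already implies one rule for both days.
- The wording is not wholly open. Clearance is expressed relative to what was deposited, and the clock runs from the start of imaging. Both point to the earliest image or images.
- The 0.77 arises only when the whole SD is image noise. With a very fast airway pool whose rate varies between days, the mean can lose to image 1. With the rest of the SD in pool size, that happens above a rate CV of about 0.58 (half-life 5 minutes) or 0.68 (10 minutes). The documents cannot exclude this.
- The mean has its own costs. Image 1 sits 1.5 to 6% above 100%, so the area starts negative unless its starting time is also set. The level moves from 28.2% to about 26.9%, away from the cited benchmark and perhaps from the scale of the 7.7.
- Nothing in the documents suggests that the reference will be picked by its p-value.

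**Conclusion.** No change to the plan follows. Neither document names the reference, but this is procedural detail that an imaging group fills sensibly, and each natural choice, used alike on both days, gives a valid comparison with the stated 6.8-point sensitivity. Choosing among the references is a trade-off that depends on the noise model. With mainly day-to-day rate variation and image CV up to 2%, the five-image mean gains about 4 to 7% in standardised effect over image 1 and does slightly worse than image 5. Its advantage over both single images appears only above a CV of about 2.2%, and reaches 29% only when all of the 7.7 SD is image noise.

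These sizes assume single-exponential clearance of 28.2% at 90 minutes, contiguous images, an effect starting at minute 10, and a 7.7 SD obtained with an image-1 reference. The documents settle neither the noise split nor the reference behind the 7.7. A sentence naming one pre-cannula reference, time zero and the start of the area would be harmless tidying, but the soundness of the analysis does not depend on it.

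### Minor: the 6.8% detectable change is for a paired t-test, but the SAP names only the Wilcoxon signed-rank test, for which it is about 7.2% (exact, two-sided, Normal differences)

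*Protocol*

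**What the plan says.** Item 7 of the MCC assessment section holds the only power statement in either document. It takes a within-subject SD of differences of 7.7% from the group's earlier measurements ("demonstrated a standard deviation of the intrasubject differences in MCC measurements"), alpha 0.05, beta 0.2 and 12 matched pairs, and concludes that "we could detect a 6.8% (absolute) change in MCC rates via paired t-test". For context it adds that differences in a published humidification study "were approximately 8% after 7 days of daily therapy". Item 8 replaces non-completers until 12 subjects have finished both days, so no dropout allowance applies.

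The SAP names one test: "Statistical comparisons will be made using paired non-parametric statistics to compare the baseline clearance day to the Airvo clearance day (Wilcoxon Signed Rank"). It does not say whether the test is exact or approximate, or one- or two-sided, and it gives no power or detectable change. The protocol names no test other than the paired t-test in item 7.

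**The concern.** The one sensitivity figure in the plan belongs to a test that the SAP does not use. A reader judging a null result would take 6.8% as the change that the trial had 80% power to find, although nobody has shown this for the signed-rank test. With 12 pairs the two tests need not agree closely. Ranking costs a little efficiency when differences are Normal, and the exact signed-rank test can attain only certain significance levels, so it may have to run below 0.05. The questions are how large the discrepancy is and whether it threatens the sample size.

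**Working it through.** **Inputs (protocol, item 7).** SD of differences 7.7%, n = 12 pairs, alpha 0.05, power 0.80. Sidedness is not stated.

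**Step 1: reproduce 6.8%.** For a two-sided paired t-test with 11 df, power at a true change δ is the probability that a noncentral t with noncentrality δ√12/7.7 exceeds 2.201.
- At 6.8% the noncentrality is 6.8 × 3.464 / 7.7 = 3.06, and power is 79.5%.
- Solving for 80% gives 6.84%. As a hand check, 7.7 × (2.201 + 0.876) / 3.464 = 6.84.
- At 8% power is 90.5%.
- Other readings do not give 6.8%: one-sided t 5.90%, two-sided normal approximation 6.23%, one-sided normal 5.53%.

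So the stated figure is right for a two-sided paired t-test.

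**Step 2: rejection rule of the signed-rank test.** Let W be the smaller rank sum. Enumerating the 2^12 sign patterns gives 2P(W ≤ 13) = 0.0425 and 2P(W ≤ 14) = 0.0522. An exact two-sided test at 0.05 must reject at W ≤ 13, with true size 0.0425.

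The large-sample version has mean 39 and variance 12 × 13 × 25 / 24 = 162.5. At W = 14:
- without continuity correction, z = 25/√162.5 and p = 0.0499, which rejects (true size 0.052);
- with correction, z = 24.5/√162.5 and p = 0.0546, which does not. The corrected version therefore has the same cut-off as the exact test.

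**Step 3: power of the signed-rank test.** By simulation, SD 7.7%, n = 12, two-sided:

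| Version and shape of differences | Power at 6.8% | Power at 8% | Change with 80% power |
|---|---|---|---|
| Paired t, Normal (for reference) | 79.5% | 90.5% | 6.84% |
| Exact, Normal | 75.3% | 87.6% | about 7.2% |
| Uncorrected approximation, Normal | 78.6% | 89.8% | about 6.9% |
| Exact, t with 10 df | 77.3% | 88.3% | 7.05% |
| Exact, logistic | 77.7% | 88.3% | 7.01% |
| Exact, t with 5 df | 80.5% | 89.8% | 6.75% |
| Exact, Laplace | 80.2% | 88.8% | 6.79% |
| Exact, uniform | 68.9% | 83.9% | 7.66% |

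**Step 4: where the gap comes from (Normal, at 6.8%).** The total is 79.5 − 75.3 = 4.2 points. A test randomised between the two cut-offs to have size exactly 0.05 would use weight (0.05 − 0.0425)/(0.0522 − 0.0425) = 0.77 on W = 14. Its power would be 0.7529 + 0.77 × (0.7862 − 0.7529) = 0.7785. Discreteness therefore costs about 2.6 points (77.85 − 75.29) and ranking about 1.7 (79.51 − 77.85).

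**Step 5: compare with uncertainty in the SD.** If the SD were 8.1% instead of 7.7%, the paired t-test alone would need about 7.2% for 80% power. That is the same shift as changing the test.

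**The case against.** Neither document makes a false statement. Item 7 labels its figure as a t-test figure and computes it correctly, and the SAP makes no power claim. Planning with a t-test and analysing with a rank test is a common approximation. The 7.2% depends on an exact test, two sides and Normal differences, none of which the SAP fixes. Other choices give anything from slightly below 6.8% to about 7.7%, and a one-sided exact test would give about 6.2%. No decision about the trial changes.

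The SD is also the less certain input. The documents do not say how many subjects lie behind 7.7%. If it were 20, a 95% interval under Normality would run from about 5.9% to 11.2%; if 40, from about 6.3% to 9.9%. The reference cited for it concerns the cystic fibrosis lung, not COPD. Against that, a correction of 0.4 points may look like false precision.

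Much of this stands. It is why the point is minor and why 7.2% should be quoted only with its conditions. It does not remove the mismatch, which rests on none of those assumptions: the approximation is acceptable when declared, and here it is not. Normality is already implied by the t-test calculation, and two sides are the only reading that reproduces 6.8%, so the exact version is the one condition added. That choice can decide the result, since W = 14 is significant with the uncorrected approximation and not with the exact test.

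**Conclusion.** The point holds, as a minor inconsistency. The only detectable change in the plan is tied to a paired t-test, the SAP names only the signed-rank test, and nothing connects them. Under item 7's inputs, Normal differences and an exact two-sided test, the matching figure is about 7.2%, with power of about 75% at 6.8%. The mismatch is certain; the 7.2% is conditional. Item 7 is not miscalculated and the trial is not shown to be too small: at the cited difference of approximately 8%, exact signed-rank power is 84% to 90% across the shapes examined.

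**What to change.** Keep the signed-rank test. Restate item 7 along these lines: *12 pairs give 80% power to detect an absolute change of about 7.2% by the exact two-sided Wilcoxon signed-rank test, assuming Normal differences with SD 7.7% (6.8% by paired t-test).* In the SAP, add exact and two-sided to the name of the test, which also settles how W = 14 would be read.

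A lighter alternative is one clause in item 7 saying that 6.8% is a t-test planning approximation and that the analysis will use the signed-rank test. This commits the protocol to no new assumption, but leaves the test version open unless the SAP is changed too.

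The cost is one sentence in the protocol and two words in the SAP. No subjects are added and the test does not change. The only downside is a slightly less favourable stated figure, still below the cited difference of approximately 8%.
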